2.2 Analysis sets

The **Full Analysis Set** (FAS) comprises all randomized participants. According to the intent-to-treat principle, participants will be analyzed according to the treatment group they have been assigned to during the randomization procedure.

The **Per-Protocol Set** is a subset of the FAS in which participants are not treated with any inclsiran if they are randomized to the usual care treatment group or do not have any major protocol deviations (including deviations from inclusion/exclusion criteria) in either treatment group.

The **Restricted Set 1** is a subset of the FAS which includes only participants without changes in background lipid-lowering therapy. A change includes starting a new lipid-lowering therapy or stopping an existing lipid-lowering therapy after the study treatment start date.

The **Restricted Set 2** is a subset of the FAS which includes only participants who received three doses of inclisiran in the inclisiran + usual care group (i.e., excludes participants in the inclisiran + usual care group who missed one or more doses) and all participants in the usual care group (including participants who may have used commercially available inclisiran).

The **Safety Set** includes all participants who received study treatment. Participants will be analyzed according to the study treatment received. Refer to [Table 2-1](#) for assignment of actual treatment for the different scenarios. Participants in the usual care treatment group who have data collected at the baseline visit will be included in the Safety Set.

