4.2 Rationale for dose/regimen and duration of treatment

Previous studies have shown that a 300 mg dose of inclisiran sodium is well tolerated and provides maximum efficacy (i.e., doses higher than 300 mg did not provide additional efficacy in LDL-C lowering). The 300 mg dose of inclisiran will be administered on Day 0, Day 90 and Day 270, consistent with the dose and dosing regimen that was studied in the Phase III trials. Modelling and simulation have demonstrated that the 300 mg dose of inclisiran results in sustained reductions in LDL-C (Ray et al 2017). A treatment duration of one year will be sufficient to assess changes in LDL-C due to inclisiran and changes in concomitant lipidlowering therapy.

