The Restricted Set 2 is a subset of the Full Analysis Set which includes only participants who received three doses of inclisiran in the inclisiran + usual care group (i.e., excludes patients in the inclisiran + usual care group who missed one or more doses) and all participants in the usual care group (including participants who may have used commercially available inclisiran).

The Safety Set includes all participants who received study treatment. Participants will be analyzed according to the study treatment received, where treatment received is defined as the randomized/assigned treatment if the participant took at least one dose of that treatment or the first treatment received if the randomized/assigned treatment was never received.

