12.4.7 Supportive analyses

The primary analysis of the two primary efficacy variables will be repeated for the Per-Protocol Set, Restricted Set 1, and Restricted Set 2.

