Data collected at scheduled or unscheduled visits will be used in the analysis if they fall into an analysis window for an analysis visit. If more than one visit (scheduled or unscheduled) is made within the window specified above for any analysis visit, the non-missing assessment closest to the target study day will be used in the analysis for that visit. In the case of tied visits, non-missing data from the later visit will be used. In the case of identical collection dates and times, the average of the two visits will be used. However, all data will be included in the participant data listings.

Last Visit Summaries

The protocol uses the term End of Study (EOS) for Day 330. If a participant discontinues from the study early, they will have an early termination visit that is before Day 330. Using the windowing provided in [Table 2-2](#), the early termination visit will be assigned to the nearest analysis visit. Tables that summarize data by visit will include data by analysis visit (Baseline, Day 90, Day 270, and Day 330) along with a Day 330/Last Visit which will combine data from Day 330 for those participants who have data collected within the Day 330 analysis window with the data from the last post-baseline visit for those participants who do not have data collected in the Day 330 analysis window.

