$$H_0: [\pi_1/(1 - \pi_1)]/[\pi_0/(1 - \pi_0)] \leq 1 \text{ versus } H_A: [\pi_1/(1 - \pi_1)]/[\pi_0/(1 - \pi_0)] > 1$$

Primary efficacy variable 2 will be analyzed at each post-baseline visit using a logistic regression model with treatment and baseline LDL-C as explanatory variables (Stokes et al. 2012). The odds ratio, two-sided 97.5% confidence interval for the odds ratio, and p-value based on the fitted model will be reported. If the p-value based on a two-sided test for inclisiran + usual care versus usual care at Day 330 is < 0.025 and the corresponding odds ratio is greater than 1, statistical significance in favor of inclisiran + usual care is shown. In case of non-

convergence of a logistic regression model, the model will be updated to use Firth's penalized likelihood method (Firth 1993). If the model using Firth's method still shows convergence issues then the baseline LDL-C covariate may be removed from the model. Two-sided 97.5% confidence intervals for the proportion of participants who achieve LDL-C < 70 mg/dL in each treatment group will be calculated, using the normal approximation to the binomial distribution.

The primary analysis of primary efficacy variable 2 will be based on the FAS. The primary analysis of this variable will be repeated for the Per-Protocol Set, Restricted Set 1, and Restricted Set 2.

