2.5.4 Handling of missing values not related to intercurrent event

For the primary analysis of primary efficacy variable 1, the MMRM implicitly imputes missing data under a missing at random assumption.

For the primary analysis of primary efficacy variable 2, participants with missing LDL-C data will be assumed to have LDL-C \geq 70 mg/dL (i.e., “non-responder”).

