5.5 Rule of exclusion criteria of analysis sets

Table 5-2 Criteria Leading to Exclusion

Analysis Set	Criteria that cause participants to be excluded
FAS	Not randomized
Restricted Set 1	Not randomized Changes in background lipid-lowering therapy
Restricted Set 2	Not randomized Less than three doses of inclisiran in the inclisiran + usual care group (miss one or more doses)
Per Protocol Set	Not randomized Treated with any inclisiran if randomized to usual care treatment group Major protocol deviations
Safety	Participants who have no data collected at baseline or any post-baseline visits.

6 Reference

Chen M, Kianifard F (2000) A nonparametric procedure associated with a clinically meaningful efficacy measure. *Biostatistics* 1(3):293-8.

Firth, D. (1993) Bias reduction of maximum likelihood estimates. *Biometrika*. 80:27-38.

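### Restricted Set 2 drops early leavers from the inclisiran arm only, so counting missing LDL-C as failure tilts its LDL-C < 70 mg/dL result towards inclisiran

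*SAP*

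**What the plan says.** SAP 2.2 says that Restricted Set 2 "includes only participants who received three doses of inclisiran in the inclisiran + usual care group". Protocol 12.1 adds "and all participants in the usual care group (including participants who may have used commercially available inclisiran"). In SAP Table 5-2 (section 5.5), apart from not being randomized, the only ground for exclusion is "Less than three doses of inclisiran in the inclisiran + usual care group (miss one or more doses"). No retention condition applies to usual care.

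Protocol 4.2 gives the dose timing: inclisiran "will be administered on Day 0, Day 90 and Day 270".

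For primary efficacy variable 2 (LDL-C < 70 mg/dL at Day 330), SAP 2.5.2 states: "The primary analysis of this variable will be repeated for the Per-Protocol Set, Restricted Set 1, and Restricted Set 2". Protocol 12.4.7 says the same and classes these repeats as supportive. The only missing-data rule for that analysis is in SAP 2.5.4: "participants with missing LDL-C data will be assumed to have LDL-C" of 70 mg/dL or more, that is, non-response.

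The Day 330 window in SAP Table 2-2 is study days 301 to 375. For a participant who discontinues the study early, "the early termination visit will be assigned to the nearest analysis visit". SAP 2.5.6 plans an observed-data version of the variable 2 analysis but does not say that it is run on Restricted Set 2.

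**The concern.** Take two participants who leave the study on the same day before Day 270, one from each arm. The inclisiran participant has fewer than three doses and is excluded from the set. The usual-care participant stays in and has no Day 330 LDL-C, so counts as a failure. The inclisiran arm sheds its early failures and the usual-care arm keeps them.

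Two things are at stake. With no true effect, the supportive table can look positive beside a negative primary result. With a real effect, the odds ratio in this set exceeds that in the Full Analysis Set (FAS) whenever any loss precedes dose 3, even if full dosing adds nothing. A reader could take that gap as a benefit of completing the dosing schedule.

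**Working it through.** **Inputs from the documents.** SAP section 3: response 0.55 (usual care) and 0.75 (inclisiran + usual care), two-sided 0.025, 1:1 allocation, 20% loss to follow-up by Day 330, 192 per arm. Protocol 4.2: dose 3 at Day 270.

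**The plan's own figures reproduce.** The pooled two-proportion z-test at 85% power gives 121 per arm, or 242. For variable 1, a difference of 15 with SD 40 gives 153 per arm, or 306. Then 153 / 0.80 = 191.25, rounded up to 192 per arm, or 384.

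**Assumptions.** Dropout is equal in the arms and unrelated to LDL-C. The share of losses before dose 3 is not in the documents and is taken as 25%, 50%, 82% (uniform dropout, 270/330) and 100% (upper bound). The 20% is a sample-size allowance, so 10% and 5% are shown too. Participants who miss a dose but still give a Day 330 value are a separate selection question and are left out.

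**Formulas.** Let m be total loss, f the share of losses before dose 3, and p1, p0 the true response rates.

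- Usual care, both sets: p0(1 − m), n = 192.
- Inclisiran, FAS: p1(1 − m), n = 192.
- Inclisiran, Restricted Set 2: p1(1 − m)/(1 − mf), expected n = 192(1 − mf).

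**Example, no effect, m = 0.20, f = 1.** Usual care: 0.55 × 0.80 = 0.44. Inclisiran: 0.44/0.80 = 0.55. Odds ratio (0.55/0.45)/(0.44/0.56) = 1.56. The FAS has 0.44 in both arms, odds ratio 1.00.

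**Example, planned effect, m = 0.20, f = 0.5.** Inclisiran: 0.60/0.90 = 0.667. Usual care: 0.44. Odds ratio 2.55. FAS: 0.60 against 0.44, odds ratio 1.91. With no missing data it is 2.45.

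**Results.** Significance means two-sided p < 0.025 favouring inclisiran (nominal 1.25%), by an unadjusted Wald test of the log odds ratio, 400,000 runs per cell. The bracket compares with 2.45.

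| Loss | Before dose 3 | OR, no effect | Significant, no effect | OR, planned effect | FAS OR, planned effect |
|---|---|---|---|---|---|
| 20% | 25% | 1.10 | 3.6% | 2.18 (−11%) | 1.91 |
| 20% | 50% | 1.22 | 9.5% | 2.55 (+4%) | 1.91 |
| 20% | 82% | 1.41 | 26% | 3.23 (+32%) | 1.91 |
| 20% | 100% | 1.56 | 42% | 3.82 (+56%) | 1.91 |
| 10% | 25% | 1.05 | 2.4% | 2.30 (−6%) | 2.12 |
| 10% | 50% | 1.11 | 4.1% | 2.50 (+2%) | 2.12 |
| 10% | 82% | 1.19 | 8.1% | 2.83 (+15%) | 2.12 |
| 10% | 100% | 1.25 | 12% | 3.06 (+25%) | 2.12 |
| 5% | 25% | 1.03 | 1.8% | 2.37 (−4%) | 2.26 |
| 5% | 50% | 1.06 | 2.4% | 2.48 (+1%) | 2.26 |
| 5% | 82% | 1.09 | 3.5% | 2.64 (+8%) | 2.26 |
| 5% | 100% | 1.12 | 4.4% | 2.74 (+12%) | 2.26 |

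At 20% loss the FAS itself is significant in 1.3% of no-effect trials. In the 82% row, 25.0 of the 26.3 points are trials in which the FAS is not significant.

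**Crossover.** The Restricted Set 2 odds ratio exceeds 2.45 when f > p1 − (1 − p1)p0/(1 − p0) = 0.75 − 0.25 × 0.55/0.45 = 0.444, whatever m is. It exceeds the FAS odds ratio for any f > 0.

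**Checks.** A simulation of the planned logistic regression with a baseline covariate (2,000 runs, no effect, 20% loss) gave 10% at f = 0.5 and 45% at f = 1, so the unadjusted test does not overstate the problem. Removing pre-dose-3 leavers from both arms brought the rate back to 1.2% to 1.4%, which identifies the one-sided exclusion as the cause. Observed Day 330 data alone give odds ratio 1.00 with 1.2% significance under no effect, and 2.45 under the planned effect, at every early share.

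**The case against.** The analysis is supportive. The primary analyses use the FAS, the Bonferroni split covers only the two primary variables, and no success claim is attached to this set. That stands and limits the severity.

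The larger figures need heavy, early loss. The 20% is an allowance, and the protocol asks participants who stop treatment to keep attending visits. If half the losses are early, the no-effect rates are 2.4% at 5% loss and 4.1% at 10%, and the planned-effect odds ratio stays within 1% to 4% of 2.45. This is fair: the direction is certain, the size is not, and the whole range should be read.

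SAP 2.1.1 adds a Day 330/Last Visit row to by-visit tables, carrying the last post-baseline value for those without Day 330 data. Variable 1 on the same set uses MMRM and is free of this mechanism. Both are partial cross-checks, but neither alters the Day 330 responder result. Likewise, someone lost after dose 3 with an LDL-C from study day 301 onwards is not missing; the bias comes from losses before dose 3, so it is unchanged.

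Finally, observed-data analysis rests on its own untestable assumption and departs from Protocol 12.4.7. It is unbiased here only because dropout was taken as unrelated to LDL-C. That also stands, and is why the non-responder version may be kept alongside and the set called descriptive.

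**Conclusion.** The concern holds. The written rules together favour inclisiran in the Restricted Set 2 analysis of LDL-C < 70 mg/dL whenever dropout is equal in the arms and some of it precedes Day 270. With no drug effect, significance favouring inclisiran runs from 1.8% (5% loss, a quarter early) to 42% (20% loss, all early) against a nominal 1.25%. Under the planned effect at 20% loss, the odds ratio is 2.18 to 3.82 where the FAS gives 1.91 under the same missing-data rule. These sizes rest on assumed dropout timing and on dropout unrelated to LDL-C. The FAS primary analysis and the variable 1 MMRM are untouched by this mechanism. It should be corrected, but no trial decision depends on it.

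**What to change.** Keep the definition of the set and add to SAP 2.5.2:

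> For Restricted Set 2, primary efficacy variable 2 will be analyzed on observed Day 330 LDL-C as in Section 2.5.6, without imputation, and this is the result to be interpreted for this set. The non-responder version, if shown, is presented beside it only for comparison with the FAS. Results in this set are descriptive, because full dosing is a post-randomization selection in one arm only.

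List the change in SAP section 4, since it departs from Protocol 12.4.7.

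The cost is three sentences, one list item and a rerun of an analysis already planned. The table would hold fewer usual-care participants: about 38 fewer at 20% loss (192 × 0.20), 19 at 10% and 10 at 5%. Bias from selecting fully dosed participants, or from dropout related to LDL-C, remains; the descriptive label tells the reader so.

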2.2.1 Subgroup of interest

Subgroup analyses of the two primary efficacy variables and the secondary endpoint of absolute change from baseline in LDL-C will be performed for the following subgroups (note that results for a subgroup category will only be presented if the total across both treatment groups within the category is at least 10 participants):

- Background lipid-lowering therapy at baseline: Yes, No
- Medical history of statin intolerance: Yes, No (from medical history statin intolerance CRF page)
- Baseline statin intensity: High, Moderate or Low, None
- Age: <65 years, >= 65 years
- Sex: Male, Female
- Race subgroup 1: White, Non-White/Multiple (unknown will be excluded from subgroup analyses)
- Race subgroup 2: White, Black or African American, Non-White/Non-Black or African American/Multiple (unknown will be excluded from subgroup analyses)
- Ethnicity: Hispanic or Latino, Not Hispanic or Latino (unknown or not reported will be excluded from subgroup analyses)
- BMI: >=30 vs < 30, and >=25 vs < 25 kg/m²
- Renal impairment by eGFR categories at baseline: <15, ≥15 to <30, ≥30 to <60, ≥60 to <90, or ≥90 mL/min/1.73m²
- Baseline LDL-C: <=100 and > 100 mg/dL; by median; and then by quartiles
- Index myocardial infarction: ST segment elevation myocardial infarction (STEMI), Non-ST-segment elevation myocardial infarction (NSTEMI), No myocardial infarction (from ACS medical history)
- Atrial fibrillation associated with index myocardial infarction: Yes, No (from ACS medical history)
- Revascularization procedure during index ACS event: Yes, No (from ACS medical history)
- History of diabetes: Yes, No (from ACS medical history)
- Baseline glycemic status: Diabetes, Pre-diabetes, Normoglycemia

For definition of baseline glycemic status, refer to Section [2.7.3, Table 2-4](#).

2.3 Patient disposition, demographics and other baseline characteristics

Summary statistics will be presented for continuous demographic and baseline characteristics and the number and percentage of participants in each category will be presented for categorical variables for each treatment group. The summaries will be reported for the FAS, if not otherwise stated.

2.3.1 Patient disposition

Participant disposition will be summarized as follows:

- The number of participants who signed the informed consent form, are screen failures, are randomized, are treated (Safety Set), completed the study or who discontinued early along with reasons for early study discontinuation, the number of screened subjects, completed screening phase and were randomized, completed screening phase but were not randomized, did not complete screening phase, and primary reason for not completing screening phase will be summarized for all screened participants.
- The number of participants in each analysis population will be summarized by treatment group for all randomized participants.
- The number of participants who complete the treatment phase or who discontinued treatment early along with reasons for early treatment discontinuation will be summarized for the inclisiran + usual care group for the FAS.
- The duration of exposure to inclisiran (in days) will be summarized for the inclisiran + usual care group for the FAS.
- The number of participants who complete the study or who discontinued the study early along with reasons for early study discontinuation will be summarized by treatment group for the FAS.
- The duration on study (number of days from study start date to study end date [last recorded contact/participation date in the database]) will be summarized by treatment group for the FAS.

The number and percentage of participants with important protocol deviations will be summarized by treatment group for the FAS.

2.3.2 Demographics and other baseline characteristics

Participant demographics including age, age category (<65 years vs ≥65 years; 18 to <50, 50 to <65, 65 to <75, ≥75 years), race, ethnicity, sex, and child bearing potential status; and baseline characteristics such as source of participant referral, smoking status by substance, body height, weight, BMI, LDL-C, and non-HDL-C will be summarized by treatment group using the FAS.

Medical history (ACS medical history, other medical history, and medical history of statin intolerance) will be summarized by treatment group using the FAS. Other medical history will

be summarized by system organ class and preferred term. Tabulation of ACS medical history will include summaries by treatment group for the following durations:

- Duration from index hospitalization discharge to informed consent: number of days from date of hospitalization discharge for the index ACS event to date of informed consent
- Duration from index hospitalization discharge to study treatment start: number of days from date of hospitalization discharge for the index ACS event to study treatment start date (Day 1)

2.4 Treatments (study treatment, rescue medication, concomitant therapies, compliance)

2.4.1 Study treatment / compliance

Study drug administration will be summarized overall and by dosing visits for the Safety Set. Summaries will also include missed doses and number of participants randomized to usual care who received at least one dose of inclisiran on study.

2.4.2 Prior, concomitant and post therapies

Concomitant medications and significant non-drug therapies prior to and after study treatment start date will be listed and summarized according to the Anatomical Therapeutic Chemical (ATC) classification system and preferred drug name, by treatment group, for the Safety Set. Additional summaries will be provided for lipid-lowering therapies. ATC Level 3 will be used for summaries of medications. If a medication is not coded at the ATC Level 3, the ATC Level 2 will be utilized. See list of lipid-lowering therapies below. Medications will be coded using the World Health Organization (WHO) drug dictionary, and will be coded/re-coded with up-version during the course of study. The final coding version used in this study will be WHODrug Global B3 March 1, 2024. Medications recorded as part of medical history will be presented separately and will not be considered in any analysis of prior or concomitant therapy.

Partially missing medication dates will be imputed following Appendix [5.1.2](#). Prior medications include all medications stopped prior to study treatment start date. Concomitant medications include any medications taken on or after study treatment start date. In case the medication date values do not allow unequivocally allocating a medication to prior or concomitant medication, the medication will be considered as concomitant medication in the statistical analysis. This rule does not apply to medications recorded on the “ACS Medical History” or the “Medical History of Statin Intolerance” CRFs as no medication dates were captured on these forms by design.

The statin intensity (none, low, moderate, high) will be defined by clinical review of the data according to American College of Cardiology/American Heart Association (ACC/AHA) classification of high intensity and based on the specific statin drug name, dose (unit), and frequency recorded in the data.

Lipid-lowering therapies (LLT) taken at baseline, changes in lipid-lowering therapies prior to baseline, concomitant lipid-lowering therapies by visit, a shift table from baseline statin

intensity level to post-baseline lipid-lowering therapy addition group, and a shift table for statin intensity from baseline to Day 330/Last Visit will also be provided. To this end, the LLTs and statin intensity for Day 330/Last Visit will be assessed on the Day 330 visit date for participants with recorded Day 330 visit date, or on the study end date (date of last participation) otherwise. For the shift table for statin intensity from baseline to Day 330/Last Visit, the “None” category includes participants who did not take statin post baseline or who stopped the statin during the study.

Changes in LLTs prior to baseline will focus on statin and bempedoic acid taken within 30 days prior to study treatment start date, i.e. any time from day -30 to day -1. Number and percentage of participants will be presented for the following statin categories: initiation of statin therapy (no statin record present at day -30), discontinuation of statin therapy (no statin record present at day -1), increase in statin intensity, decrease in statin intensity, and change of statin within the same intensity group. Treatment gaps and/or overlapping treatment periods in case of two or more statins within the 30-day period will be ignored for analysis. If at least one statin record is present indicating that the statin was taken consistently on all days within the 30-day period, the participant will not be considered as having had any change in statin therapy.

For the analysis of lipid-lowering therapies at baseline a modified lipid-lowering therapy definition is also employed. For this analysis a modified lipid lowering therapy includes any statin, ezetimibe, PCSK9 inhibiting monoclonal antibodies, or bempedoic acid therapies.

The following medications will be included in the lipid-lowering therapy tables.

Table 2-3 Lipid-lowering Therapies

Medication	Medications included
Lipid Lowering Therapy	ATCCODE2=C10
Statin	ATCCODE2=C10 and CMDECOD contains ‘statin’, or ATCCODE4=C10AA, C10BA, or C10BX
Ezetimibe	ATCCODE2=C10 and CMDECOD contains ‘ezetimibe’
PCSK9 inhibiting monoclonal antibodies	ATCCODE2=C10 and CMDECOD contains ‘evolocumab’ or ‘alirocumab’
Bempedoic acid	ATCCODE2=C10 and CMDECOD contains ‘bempedoic acid’
Modified lipid lowering therapy	ATCCODE2=C10 and CMDECOD contains ‘statin’, ‘ezetimibe’, ‘evolocumab’, ‘alirocumab’, or ‘bempedoic acid’

